## 6. STUDY INTERVENTION

### 6.1. Identity of Test Articles

Table 2: Artificial Tears

	Test	Control
Solution Name/Description	Investigational lipid eye drops (9618X)	Blink® Tears
Manufacturer	Johnson & Johnson Vision, Inc	Johnson & Johnson Vision, Inc
Ingredients	Castor Oil, Polyoxyl 40 Hydrogenated Castor Oil, Sodium Chlorite, Boric Acid, Sodium Borate Decahydrate, Sodium Chloride, Potassium Chloride, Calcium Chloride Dihydrate, Magnesium Chloride Hexahydrate, Polyethylene Glycol 400, Sodium Hyaluronate, Purified Water	Sodium Chlorite Boric Acid Sodium Borate Decahydrate Sodium Chloride Potassium Chloride Calcium Chloride Dihydrate Magnesium Chloride Hexahydrate Polyethylene Glycol 400 Sodium Hyaluronate Purified Water
Packaging Form	Over-Labeled	Over-Labeled

## 6.2. Ancillary Supplies/Products

ScleralFil (Bausch + Lomb), LacriPure (Menicon) and Fluorescein (Akorn, Inc.), or other country-specific alternative approved by the sponsor.

Table 2: Ancillary Supplies

Solution			
Solution Name/Description	ScleralFil (or other sponsor-approved product)	Lacripure (or other sponsor-approved product)	Fluorescein (or other sponsor-approved product)
Manufacturer	Bausch + Lomb	Menicon	Akorn, Inc
Preservative	None	None	None
Other distinguishing items (dye, packaging, approval status, etc.)	NA	NA	D&C Yellow No. 8, 0.6 mg

Sodium fluorescein dye will be used for biomicroscopy, as needed. Sterile, preservative-free, saline may be used in this clinical study to rinse each eye.

## 6.3. Administration of Test Articles

Test articles will be dispensed to subject meeting all eligibility requirements, including any dispensing requirements set forth in this clinical protocol. Subjects will be dispensed an adequate supply of test articles to complete the study. Lost or damaged test articles will not be replaced at the discretion of the Investigator and/or the Sponsor.

## 6.4. Packaging and Labeling

The test articles will be packaged in bottles as the primary packaging. The test article will be over-labeled to mask the subject to the identity. The test articles will be in investigational cartons sealed with a tamper evident seal, commercial cartons, or in plastic bags as the secondary packaging form. The labels for the primary and secondary packages will contain the following message, in accordance with J JV over-labeling procedures for masked studies involving marketed products: "For Use in Clinical Study CR-6328 Only, Not for Resale. Product Conforms to with CE Mark Requirements." The labels will also contain the product code, lot number, expiration date and the clinical study number.

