### 1.1. Name and Descriptions of Investigational Products

The products used in this clinical study are listed below:

- Investigational lipid eye drops 9618X (Test)
- Blink® tears eye drops (Control)

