### **5.2. Masking**

This is a double-masked study where subjects and the investigators are masked to the identity of the eye drops during the study period. Every attempt will be made to keep the other clinical trial personnel involved in the study (e.g., Data management, Biostatistician) unaware of the identity of the test articles.

The identity of the investigational products will be masked by over labeling the eye drop bottles with a label containing the study number, expiration date and the randomization codes. Only the personnel involved in the over labeling and the unmasked Statistician generating the randomization scheme will have access to the decode information translating the randomization codes into Test and Control eye drops. The medical monitor will also have access to the decode information in case breaking the mask is necessary for the urgent medical treatment of a subject.

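### Sections 5.2 and 6.4 describe different masking labels, and the one in 6.4 could let site staff identify or group the arms

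*Combined protocol and SAP*

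**What the plan says.** Section 5.2 (Masking) states that "subjects and the investigators are masked to the identity of the eye drops during the study period". Identity is concealed by "over labeling the eye drop bottles with a label containing the study number, expiration date and the randomization codes". The decode is held only by the over-labeling personnel, the unmasked statistician and the medical monitor.

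Section 6.4 (Packaging and Labeling) gives a narrower purpose: "The test article will be over-labeled to mask the subject to the identity". It prescribes a study-use message for primary and secondary packs, citing the sponsor's "over-labeling procedures for masked studies involving marketed products", and then adds: "The labels will also contain the product code, lot number, expiration date and the clinical study number". The outer pack may be a sealed investigational carton, or "commercial cartons, or in plastic bags as the secondary packaging form".

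Section 1.1 identifies one arm as "Investigational lipid eye drops 9618X (Test)". The same identifier appears in the synopsis, section 1 and section 6.1. Section 1.2 describes Test as investigational and Control as an approved, marketed product. Section 6.1 gives the packaging form of both arms as over-labeled.

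**The concern.** Whoever prepares the packs cannot tell from the protocol which label to print. The two lists share only the study number and the expiry date. The item that carries the mask in 5.2, the randomization code, is missing from 6.4. The two items that 6.4 adds, product code and lot number, are of a kind that ordinarily belongs to a product.

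Site staff hold the protocol, handle the bottles and carry out the assessments. Corneal staining of Grade 2 or higher, a secondary endpoint, is graded at the slit lamp. Reported ocular symptoms, another secondary endpoint, come from a verbal open-ended question. The primary endpoint is a comfort rating made by the subject. Section 4.2 relies on masking to reduce bias, so a label that weakens the mask bears on all three, most directly on the staining grade.

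**Working it through.** **1. The two labels side by side**

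| Item | 5.2 | 6.4 |
|---|---|---|
| Study number | listed | listed |
| Expiration date | listed | listed |
| Randomization code | listed | not listed |
| Product code | not listed | listed |
| Lot number | not listed | listed |
| Who is masked | subjects and investigators | subject |
| Same outer pack in both arms | not addressed | not required; three forms allowed |

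**2. What each added item could reveal**

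- *Product code.* The term is not defined. The only code the protocol gives for an arm is 9618X, for Test. The Control package insert in Appendix C carries a string of the same format, 9587X, whose meaning is not given. If the printed code is of this kind, anyone holding the protocol can read the arm from the bottle. If it is a masked code, this route closes.
- *Lot number.* The two formulations differ (section 6.1). If the lot is a manufacturing lot, it would ordinarily differ between them. It would not name the product, but it would let staff group subjects. One emergency unmasking (sections 5.3 and 13.4.1) could then identify others with the same lot. If it is a packaging lot common to both arms, this route closes.
- *Outer pack.* Only Control is marketed, so a commercial carton suggests Control unless its branding is covered and both arms use the same form.

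**3. Who would see it**

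Under section 5.3 the investigator or designee consults the randomization scheme and pulls the articles from supply. Under section 12 the lot number and the subject identifier are collected together for each product complaint. The exposure is therefore mainly at the site. A subject in a parallel-group trial normally sees one product.

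**4. Size: a sensitivity range only**

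The documents give no figure for bias. The inputs from sections 2.3 and 14.2 are margin 20, SD 35, two-sided 0.05 (one-sided 0.025), power 85% and 56 per arm.

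The plan's own figure reproduces with a true difference of 0. The normal approximation is 2 × (1.960 + 1.036)² × 35² / 20² = 54.99, so 55 per arm. The exact two-sample t calculation gives 56 per arm, with power 85.02%. The labeling point does not change this.

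With 56 per arm the standard error of the difference is 35 × √(2/56) = 6.61, and the critical t on 110 degrees of freedom is 1.982. Suppose a bias of b points in the Test-minus-Control comfort difference. If it favours Test, the type I error at a true difference of −20 comes from a noncentral t with noncentrality b/6.61. If it disfavours Test, the power at a true difference of 0 uses (20 − b)/6.61.

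| Assumed b (points) | Type I error, bias towards Test | Power, bias against Test |
|---|---|---|
| 0 | 2.5% | 85.0% |
| 2 | 4.8% | 77.0% |
| 5 | 11.3% | 61.3% |
| 10 | 32.2% | 32.2% |

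These rows show how sensitive the primary test is to a given bias. They do not estimate the bias in this trial. No comparable calculation is possible for staining, because the documents give no expected rates.

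**The case against.** The strongest reply is that the two lists do not exclude each other. Section 5.2 does not say that its label carries nothing else, and 6.4 says what the labels will also contain, so one label could meet both. The product code may be a masked code. That would fit the restricted decode in 5.2 and the masked-study over-labeling procedures cited in 6.4, which are not in the documents. Section 6.1 lists both arms as over-labeled, the study message goes on outer packs as well, and nothing assigns commercial cartons to Control alone. The lot number also has a job: section 12 requires it for every product complaint.

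Most of this stands, and it rules out the stronger reading that a reader might infer, namely that 6.4 makes the arms distinguishable and the trial is not double-masked. That would need the product code to be 9618X or the lot to be product-specific, and the documents establish neither. Nor does a lot number alone tell a subject which product they have, so a direct effect on the primary VAS is not shown.

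The reply does not remove the need for a change. A label that meets both lists still shows site staff a product code and a lot number that the protocol nowhere says are masked. In 6.4 the procedures are cited for the study message, while the code and lot come in a separate sentence. No text requires matching outer packs or covered branding, and 6.4 leaves investigators out of the stated purpose.

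**Conclusion.** The concern holds as a discrepancy with a conditional risk to masking. Sections 5.2 and 6.4 differ on label contents and on whom the over-label masks, and 6.4 allows outer packs that need not match. Site staff could identify or group the arms if the product code is the identifier printed in the protocol, or if the lot is a product-specific manufacturing lot. Investigator-graded staining is the most exposed endpoint; spill-over to the self-rated primary VAS is possible through contact with site staff.

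The size and direction of any bias cannot be derived from the documents. The range of 0 to 10 points used above is assumed, and bias in either direction would matter. The change should be made because it is specific and cheap before packaging, and because a mask that has been broken is hard to detect or correct afterwards.

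**What to change.** 1. Rewrite 6.4 to match 5.2: bottles and outer packs show the study number, a kit or randomization number, and the expiry date, common to both arms where possible.
2. Keep the product code and manufacturing lot off any label that the site can see, and hold them on the decode list.
3. Require identical plain outer packs in both arms. Delete the commercial-carton option, or require all branding to be fully covered.
4. State in 6.4 that the over-label masks investigators as well as subjects.
5. Amend section 12 so that the lot number for a complaint is traced from the kit number by personnel who already hold the decode, without returning it to the site.

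The cost is revised label text, a kit list and short edits to 6.4 and section 12 before packaging. The drawback is that sites can no longer read the lot from the bottle, so each complaint needs a look-up by decode holders.

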## **6.5. Storage Conditions**

Test articles will be maintained at ambient temperatures at the clinical site. Test articles must be kept under secure conditions.

## **6.6. Collection and Storage of Samples**

When possible, any test article associated with an Adverse Events and/or a Product Quality Complaint must be retained pending directions from the sponsor for potential return back to J JV.

## **6.7. Accountability of Test Articles**

J JV will provide the Investigator with sufficient quantities of study articles and supplies to complete the investigation. The Investigator is asked to retain all shipment documentation for the test article accountability records.

Test article must be kept in a locked storage room, accessible only to those assigned by the Investigator for dispensing. The Investigator may delegate this activity to authorized study site personnel listed on the Site Delegation Log. All test articles must be accounted. This includes:

1. What was dispensed for the subject
2. What was returned to the Investigator unused
3. The number and reason for unplanned replacements

The Investigator will collect all unused test articles from the subjects at the end of the subject's participation. Subject returned unused test articles must be separated from the clinical study inventory of un-dispensed test articles and must be labeled with the subject number and date of return. Following final reconciliation of test articles by the monitor, the Investigator or monitor will return all unused test articles to J JV.

If there is a discrepancy between the shipment documents and the contents, contact the study monitor immediately.

[REDACTED]

## 7. STUDY EVALUATIONS

### 7.1. Time and Event Schedule

Table 3: Time and Events

Visit Information	Visit 1 Baseline, dispense drop	Visit 2 Follow-up #1	Visit 3 Follow-up #2
Time Point	Day 0	7+-1 days after V1	30+-2 days after V1
Estimated Visit Duration	2.5 hours	1 hours	1 hours
Study Informed Consent	X		
Inclusion/Exclusion Screening Criteria	X		
Demographics	X		
Medical History & medication review	X	X	X
Habitual Artificial Tear usage	X		
Biomicroscopy	X	X	X
Eligibility	X		
Randomization	X		
VAS questionnaire	X	X	X
PRO Questionnaire	X	X	X
Non-invasive tear break up time	X	X	X
Drop instillation	X		
Ocular Symptoms	X	X	X
Drop Dispensing & Instruction	X	X	
Drop Usage questions	X	X	X
Exit Slit-lamp		X	X
Adverse Event Review		X	X
Final Evaluation			X

## 7.2. Detailed Study Procedures

### VISIT 1

Aim for Visit 1 to occur in the afternoon (after 12 PM). The subjects must present to Visit 1 wearing their spectacles (if applicable). Subjects will be asked to bring their habitual artificial tears with them to the visit (if applicable).

Visit 1: Screening		
Step	Procedure	Details
1.1	Statement of Informed Consent	Each subject must read, understand, and sign the Statement of Informed Consent and Privacy Statement before being enrolled into the study. The Principal Investigator or their designee conducting the informed consent discussion must also sign the consent form.  Note: The subject must be provided a signed copy of this document.
1.2	Demographics	Record the subject's date of birth, gender, race and ethnicity.
1.3	Medical History and Concomitant Medications	Questions regarding the subjects' medical history and concomitant medications.
1.4	Artificial Tear Use	The subject will be asked about their artificial tear use.
1.5	Eligibility after Screening	All responses to Screening Inclusion Criteria questions must be answered "yes" and all responses to Exclusion Criteria must be answered "no" for the subject to be considered eligible.

Visit 1: Baseline		
Step	Procedure	Details
1.6	Entrance Visual Acuity	Record the distance high contrast visual acuity to the nearest letter (OD, OS, and OU) with their habitual spectacle correction in place (or unaided if applicable).
1.7	Baseline SROS	Subjects will respond to a verbal open-ended symptoms questionnaire.
1.8	Baseline VAS	The subject will respond to the VAS questionnaire
1.9	Baseline PRO questionnaires	The subject will complete the electronic questionnaires using the Kiosk portal.
1.10	Tear break-up time	Record the tear film stability (NITBUT), OD and OS, with a Medmont or other topographer.

Visit 1: Baseline			
Step	Procedure	Details	
1.11	Slit Lamp Biomicroscopy	
The FDA slit lamp classification scale will be used to grade the findings and determine eligibility.
 
If there are any Grade 3 or higher other slit-lamp findings, the subject is ineligible to continue at this time, but may return up to one additional time to determine eligibility. If discontinued a final examination must be completed.
 
If there are no slit lamp findings, and the clearance of the fluorescein needs to be expedited, preservative-free rewetting drops or saline may be instilled.
	
1.12	Expanded Sodium Fluorescein Corneal Staining	Corneal Staining Assessment (FDA grading scale) will be assessed using a more detailed scale for internal purposes only.	
1.13	Eligibility after Baseline	All responses to Inclusion Criteria questions must be answered "yes" and all responses to Exclusion Criteria questions must be answered "no" for the subject to be considered eligible.	

Visit 1: Dispensing			
Step	Procedure	Details	
1.14	Wash out	Allow a washout of at least 5 minutes from the end of the slit-lamp exam before instilling the artificial tear	
1.15	Randomization	Subjects will be randomized to an artificial tear drop (Test or Control).	
1.16	Drop instillation	
The subject will instill 1 drop in both eyes (or drops can be instilled by the investigator should the subject require drop installation training).
 
The investigator should observe the subject's technique for drop instillation and recommend new techniques to improve subject safety, if necessary.
	
1.17	Ocular Symptoms	Subjects will respond to a verbal open-ended symptoms questionnaire.	
1.18	Drop Settling	Allow the drop to settle for 5 minutes.	
1.19	VAS Questionnaire	The subject will respond to the VAS questionnaire	

Visit 1: Dispensing			
Step	Procedure	Details	
1.20	PRO Questionnaire	The subject will complete the electronic questionnaires using the Kiosk portal.	
1.21	Exit Visual Acuity	Record the distance high contrast visual acuity to the nearest letter (OD, OS, and OU) with their habitual spectacle correction in place (or unaided if applicable).	
1.22	Continuance	For the subject to continue in the study, they must meet both of the following criteria: 
 
• Visual acuity is 20/30 or better OD and OS
 
• Subject willing to use the drop 3-4 times a day OU for 7 +/- 1 days.
 
	
1.23	Instillation of drops training, if necessary	Instruct and teach instillation of drops.	
1.24	Dispense	The artificial tears will be dispensed for a 7 +/- 1 day dispensing period 
 
• Dispense enough artificial tears to last the whole week.
 
• A patient instruction guide will be provided and the subject will be instructed not to use other artificial tears during the dispensing period.
 
• Subjects will be scheduled for Visit 2 in approximately 7 +/- 1 days.
 
	

## VISIT 2

2.14.	Dispense	
Dispense enough artificial tears to last until the next scheduled visit.
 
The subject will be instructed not to use other artificial tears during the dispensing period. Subjects will be scheduled for Visit 3 to ensure the visit is completed 28 to 32 days after V1.
	

### VISIT 3

Aim for Visit 3 to occur in the afternoon (after 12 PM). The subjects must present to visit 3 wearing their habitual spectacles (if applicable) having used the study drop in both eyes at least 2 times that day.

Visit 3: 30-day Follow-up			
Step	Procedure	Details	
3.1.	Adverse Events and Concomitant Medications Review	Review any changes to the subject's medical history or concomitant medications from the previous study visit. Record any changes, and any adverse events.	
3.2.	Artificial Tear compliance	Confirm the subject used the drops as instructed.	
3.3.	Collection of Study drops	The site will collect and discard the bottle of study eye drops.	
3.4.	Subject Reported Ocular Symptoms	Subjects will respond to a verbal open-ended symptoms questionnaire.	
3.5.	VAS Questionnaire	The subject will respond to the VAS questionnaire	
3.6.	PRO Questionnaire	The subject will complete the electronic questionnaires using the Kiosk portal.	
3.7.	Preference Question	The subject will complete the electronic preference questions using the Kiosk portal, if applicable.	
3.8.	Entrance visual acuity	Record the distance high contrast visual acuity to the nearest letter (OD, OS, and OU) with their habitual spectacle correction in place (or unaided if applicable).	
3.9.	Tear Break up Time	Record the tear film stability (NITBUT), OD and OS, with a Medmont or other topographer.	
3.10.	Slit Lamp Biomicroscopy	
The FDA slit lamp classification scale will be used to grade the findings.
 
All ocular adverse events must be followed to resolution.
 
If the clearance of the fluorescein needs to be expedited, preservative-free rewetting drops or saline may be instilled.
	
3.11.	Expanded Sodium Fluorescein Corneal Staining	Corneal Staining Assessment (1.0 scale units) will be assessed using a more detailed scale for internal purposes only.	

### FINAL EVALUATION

The final evaluation will ordinarily take place immediately following the last scheduled follow-up visit per the study protocol. It may also take place at any point the subject discontinues the study or is terminated from the study.

Final Evaluation			
Step	Procedure	Details	
F.1	Final Exam Form	Indicate if the subject completed the study successfully. If subject discontinued from the study indicate the reason.	
F.2	Exit Distance Visual Acuity	Record the exit distance visual acuity OD, OS, OU with the subject's spectacles or unaided (the same method as used in Visit 1 Baseline entrance distance visual acuity).	

### 7.3. Unscheduled Visits

If, during the investigation, a subject requires an unscheduled visit to the clinical site, the following information will be collected at a minimum:

- Chief complaint prompting the visit. If the reason is an adverse event, the applicable eCRF for the adverse event must be completed and subject record completed as appropriate
- Date and time of the visit and all procedures completed at the unscheduled visit
- Review of adverse event and concomitant medications
- Documentation of any test article dispensed or collected from the subject, if applicable
- Slit lamp findings (using the Slit Lamp Classification Scale)

If the Investigator withdraws a subject from the study, the final study visit case report forms must be completed indicating the reason(s) why the subject was withdrawn. The subject record must be completed documenting the date and primary reason for withdrawal and the study CRA notified.

Any ocular and non-ocular adverse events that are ongoing at the time of the study visit will be followed by the Investigator, within licensure, until they have resolved, returned to pre-treatment status, stabilized, or been satisfactorily explained. If further treatment i.e., beyond licensure is required, the subject will be referred to the appropriate health care provider.

The following information will be collected during an unscheduled visit (when applicable)

Unscheduled Visit			
Step	Procedure	Details	
U.1	Chief Complaints	Record the subject's chief complaints for reasons for the unscheduled visit.	
U.2	Adverse Events and Concomitant Medications Review	Review any changes to the subject's medical history or concomitant medications from the previous study visit. Record any changes, and any adverse events.	
U.3	Entrance VA	Record the distance high contrast visual acuity to the nearest letter (OD, OS, and OU)	

Unscheduled Visit			
Step	Procedure	Details	
		with their habitual spectacle correction in place (or unaided if applicable).	
U.4	VAS Questionnaire	The subject will respond to the VAS comfort questionnaire	
U.5	Slit Lamp Biomicroscopy	
The FDA slit lamp classification scale will be used to grade the findings.
 
(All ocular AE's must be followed to resolution)
 
If the clearance of the fluorescein needs to be expedited, preservative-free rewetting drops may be instilled.
	
U.6	Dispensing	Dispensing of additional artificial tear drops, if necessary	
U.7	Exit Visual Acuity	Record the distance high contrast visual acuity to the nearest letter (OD, OS, and OU) with their habitual spectacle correction in place (or unaided if applicable).	

